1.1.2 Secondary Objectives

• Estimate plasma concentrations of MDGN-002 administered by SQ injection to adults with moderate to severe, active CD or UC.

• Evaluate response to treatment with MDGN-002 administered by SQ injection to adults with moderate to severe, active CD or UC.

2. STUDY DESIGN AND PROCEDURES

This is a Phase 1b, open-label, dose-escalation, signal-finding, multi-center study to evaluate the safety, tolerability, pharmacokinetics, and short-term efficacy of MDGN-002 in adults with moderate to severe, active CD or UC who have previously failed anti-TNFα treatment. The study is a pilot study using a dose-escalation design to characterize the safety and tolerability of 2 different doses of MDGN-002 (1.0 mg/kg and 3.0 mg/kg) in the CD population, and 3.0 mg/kg in the UC population. All subjects will receive a total of 4 doses of MDGN-002 by SQ injection at 14-day intervals. The study will consist of a screening period, an open-label treatment period and a safety follow-up visit.

In this document, MDGN-002 will be referred to as "study drug" regardless of dosage, and "cohort" will refer to 1.0 mg/kg (Cohort 1) or 3.0 mg/kg (Cohort 2) as described above.

The following study visits will be performed:

- Visit 1 (Screening). This period may be up to 14 weeks, inclusive of a washout period for subjects who have received a biologic treatment within 12 weeks of Visit 1. The amount of time required is determined based on the subject's last dose of the medication and may be up to 12 weeks.
- Visit 2 (Pre-/Post-Dose Day 0);
- Visit 3 (Day 7);
- Visit 4 (Pre-/Post-Dose Day 14);
- Visit 5 (Day 21);
- Visit 6 (Pre-/Post-Dose Day 28);
- Visit 7 (Day 35);
- Visit 8 (Pre-/Post-Dose Day 42);
- Visit 9 (Day 49);
- Visit 10 (Day 56/Early Termination (ET));
- Visit 11 (Day 84 or 28 days after ET).

3. DETERMINATION OF SAMPLE SIZE

This is the first use of MDGN-002 in the intended population of patients with CD or UC who have failed prior treatment with an anti-TNF α agent. The sample size of the study was based on feasibility.

4. STUDY ASSESSMENTS

4.1 CROHN'S DISEASE ACTIVITY INDEX (CROHN'S DISEASE PATIENTS)

The Crohn's Disease Activity Index (CDAI) consists of the following 8 items: abdominal pain, number of liquid stools, general well-being, extraintestinal complication, use of antidiarrheal drugs, abdominal mass, hematocrit, and body weight. Information on abdominal

pain, general well-being, and frequency of loose and watery stools will be taken from a daily diary completed by the subject.

Total CDAI scores can range from 0 to approximately 600 with higher scores indicating more active disease. Disease severity as measured by CDAI is categorized as: Remission (<150), Mildly active disease (150 - 219); Moderately active disease (220 - 450); Severe disease (> 450).

Item and total scores, as outlined below, will be derived programmatically for Visit 1 (Screening), Visits 2 (Day 0), 4 (Day 14), 6 (Day 28), 8 (Day 42), and Visit 10 (Day 56/ET).

The CDAI total score consists of 8 item scores:

- 1) The liquid stools score is calculated as the sum of the number of loose/watery stools values recorded for the 7 days prior to the visit;
- 2) The abdominal pain score is calculated as the sum of the abdominal pain values recorded for the 7 days prior to the visit. Abdominal pain severity (graded from 0 3 with higher values indicating greater severity) summed over the previous 7 days, where 0 = "None", 1 = "Mild", 2 = "Moderate", 3 = "Severe";
- 3) The general well-being score is calculated as the sum of the general well-being values recorded for the 7 days prior to the visit. General well-being is graded from 0 4 with higher values indicating a poorer condition of health, where 0 = "Generally well", 1 = "Slightly under par", 2 = "Poor", 3 = "Very poor", 4 = "Terrible";
- 4) The extraintestinal complications score is calculated as the number of complications present (0 to 6) from the following list:
 - Arthritis/arthralgia
 - Iritis/uveitis
 - Skin/mouth lesions
 - Peri-anal disease
 - Other fistula
 - Fever >37.8 °C, >100 °F (in the last week);
- 5) Taking medication for symptomatic relief from diarrhea (0 = No, 1 = Yes);
- 6) Presence of an abdominal mass (0 = None, 2 = Questionable, 5 = Definite);
- 7) Hematocrit score is calculated as follows, adding to or subtracting from total score according to sign:
 - 47 minus hematocrit value for males
 - 42 minus hematocrit value for females;

8) Weight percentage difference from standard weight, is calculated by $100 \times (1 - (\text{current weight} / \text{standard weight}))$ where the standard weight is defined as height in $m^2 \times 22.1$ for males and height in $m^2 \times 20.8$ for females. Values > 0 and indicate the subject is below standard weight; values < 0 indicate that the subject is over standard weight.

The CDAI total score is calculated as the weighted sum to the above 8 scores as follows:

CDAI =
$$2 \times (\text{Item 1}) + 5 \times (\text{Item 2}) + 7 \times (\text{Item 3}) + 20 \times (\text{Item 4}) +$$

 $30 \times (\text{Item 5}) + 10 \times (\text{Item 6}) + 6 \times (\text{Item 7}) + 1 \times (\text{Item 8})$

Please refer to section 5.7 for handling missing data.

4.2 MODIFIED MAYO SCORE (ULCERATIVE COLITIS PATIENTS)

The Modified Mayo Score (excluding the Physician's Global Assessment [PGA] component) includes stool frequency, rectal bleeding, and the appearance of mucosa upon endoscopy. Stool frequency is based on a scale of 0 to 3 (0 = "normal", 1 = "1 to 2 stools/day > normal", 2 = "3 to 4 stools/day > normal", 3 = "> 4 stools/day > normal"). Rectal bleeding will be based on a scale of 0 to 3 (0 = "none", 1 = "streaks of blood", 2 = "obvious blood", 3 = "blood alone passed"). Appearance of mucosa upon endoscopy will be based on a scale of 0 to 3 (0 = "normal", 1 = "mild friability", 2 = "moderate friability", 3 = "exudation, spontaneous bleeding"). The score consists of the sum of all 3 criteria and can range from 0 to 9, with higher scores indicating more severe disease. This score will be derived programmatically for Visit 1 and Visit 10 using the Modified Mayo Endoscopic score from the central reader and self-reported data on stool frequency and rectal bleeding from 7 days prior to Visit 1 (Screening) and Visit 10 (Day 56/ET).

4.3 ENDOSCOPY WITH BIOPSY AND HISTOLOGY

All subjects who enroll in the study will undergo an endoscopy with biopsy at screening and again at Visit 10 (Day 56) or at early termination.

Endoscopy evaluation for patients with CD will use the Simple Endoscopy Score for Crohn's Disease (SES-CD). The SES-CD is assessed through endoscopic review of 5 predefined gastrointestinal (GI) segments (ileum; right colon; transverse colon; left colon; rectum). For each segment, 4 endoscopic variables are assessed (presence of ulcers, ulcerated surface, affected surface, and presence of narrowing). Each variable is scored from 0 to 3 with higher scores indicating more severe symptoms as defined below (Daperno et al 2004).

SES-CD Score

Variable 0		1	2	3
Size of ulcers	None	Aphthous ulcers (0.1–<0.5 cm)	Large ulcers (0.5–2 cm)	Very large ulcers (> 2 cm)
Ulcerated None surface		< 10%	10–30%	> 30%

Affected surface	Unaffected segment	< 50%	50–75%	> 75%
Presence of narrowing	None	Single, can be passed	Multiple, can be passed	Cannot be passed

For each variable, the total score is calculated as the sum across all segments of the GI tract. The SES-CD total score, ranging from 0-60, is calculated as the sum of all variable total scores with a higher score indicating more severe endoscopic activity as shown (Moskovitz et al 2007).

SES-CD Score	Severity Category
0-2	Remission
3-6	Mild endoscopic activity
7-15	Moderate endoscopic activity
>15	Severe endoscopic activity

Endoscopic evaluation for patients with UC will use the Modified Mayo Endoscopic Score. Appearance of mucosa (friability) upon endoscopy will be based on a scale of 0 to 3 (0 = "normal", 1 = "mild friability", 2 = "moderate friability", 3 = "exudation, spontaneous bleeding").

4.4 PATIENT-REPORTED ASSESSMENT OF ABDOMINAL PAIN AND STOOL FREQUENCY (CROHN'S DISEASE PATIENTS)

All CD subjects who enroll in the study will be required to report their daily assessment of abdominal pain, general well-being and stool frequency including loose and/or watery stools via an electronic diary. Derived 7-day interval average scores, explained in Section 5.8 for Time Windowing, will be provided that correspond to all visits from Visit 1 (Screening) to Visit 10 (Day 56/ET).

Abdominal pain will be assessed on a scale of 0 to 3 with higher values indicating greater pain severity: 0 = "None", 1 = "Mild", 2 = "Moderate", 3 = "Severe".

The stool frequency including number of loose and/or watery stools per day, equivalent to a score of a 6 or 7 on the Bristol Stool Scale, will be recorded.

General well-being will be assessed on a scale of 0 to 4 with higher values indicating a poorer condition of health: 0 = "Generally well", 1 = "Slightly under par", 2 = "Poor", 3 = "Very poor", 4 = "Terrible".

4.5 PATIENT-REPORTED ASSESSMENT OF STOOL FREQUENCY AND RECTAL BLEEDING (ULCERATIVE COLITIS PATIENTS)

All UC subjects who enroll in the study will be required to report their daily assessment of stool frequency and rectal bleeding via an electronic diary. Derived 7-day interval average scores, explained in Section 5.8 for Time Windowing, will be provided that correspond to all visits from 1 (Screening) to 10 (Day 56/ET).

Stool frequency will be based on a scale of 0 to 3 (0 = "normal", 1 = "1 to 2 stools/day > normal", 2 = "3 to 4 stools/day > normal", 3 = "> 4 stools/day > normal"). Normal is defined as the patient's bowel movement pattern during a period of remission where remission means that their symptoms of UC resolve, they feel well, and their UC is not interfering with daily activities. If the subject has not achieved remission, then normal is their bowel movement pattern when healthy prior to being diagnosed with Ulcerative Colitis.

Rectal bleeding is to be reflective of the most severe bleeding of the day and will be based on a scale of 0 to 3 (0 = "none", 1 = "streaks of blood", 2 = "obvious blood", 3 = "blood alone passed"). If the subject had no stools in a day, then "None" would be selected.

4.6 QUALITY OF LIFE ASSESSMENT – INFLAMMATORY BOWEL DISEASE QUESTIONNAIRE

The IBD-Q is a 32-item questionnaire validated to measure quality of life in CD and UC subjects. The IBD-Q will be completed by all subjects at screening (Visit 1), before dosing (Visit 2), and at the end of the open-label treatment period or early termination (Visit 10/ET). The IBD-Q assesses the dimensions of bowel function, emotional status, systemic symptoms, and social function (Guyatt G, 1989).

Each of the 32 items is scored on a 1 to 7 scale, where higher scores represent a more positive response. The mapping of questionnaire items to each domain is given in the table below.

Domain Name	Questionnaire items
Bowel symptoms	1, 5, 9, 13, 17, 20, 22, 24, 26, 29
Systemic symptoms	2, 6, 10, 14, 18
Emotional status	3, 7, 11, 15, 19, 21, 23, 25, 27, 30, 31, 32
Social functioning	4, 8, 12, 16, 28

Each domain score is calculated as the sum of the items in that domain. The IBD-Q total score is calculated as the sum of all 32 items in the questionnaire, ranging from 32 to 224.

5. GENERAL ANALYSIS AND REPORTING CONSIDERATIONS

Descriptive statistics will be used to summarize all safety, pharmacokinetic, efficacy, and quality of life variables.

Continuous data will be summarized using descriptive statistics: n, mean, standard deviation, median, minimum, and maximum unless otherwise noted. The mean and median will be rounded to one decimal place greater that in the raw data; the standard deviation will be rounded to two decimal places greater than in the raw data; the minimum and maximum will be reported to the same number of decimal places as present in the raw data. These will be referred to as "continuous summaries" in this document.

Categorical variables will be summarized using frequency counts and percentages. When count data are presented, the percentage for zero counts will be suppressed to draw attention to the non-zero counts. Unless otherwise noted the denominator for all percentages within the analysis set of interest will be the number of subjects by disease and cohort as shown below:

	Crohn's Disease	Ulcerative Colitis	
Cohort 1	Cohort 2		Cohort 2
1 mg/kg	3 mg/kg	Tota1	3 mg/kg
(N = xx)	(N = xx)	(N = xx)	(N = xx)

Frequency counts will be presented as whole numbers and percentages will be rounded to one decimal place. These will be referred to as "categorical summaries" in this document.

5.1 BASELINE AND CHANGE FROM BASELINE MEASUREMENTS

The baseline measurement will be defined as the last non-missing assessment on the day of or prior to first study dose administration (includes all data up to the first dose administration).

Change from baseline will be calculated as:

• (value at analysis visit – baseline value)

A positive change signifies an increase in the measurement while a negative change signifies a decrease.

5.2 STUDY DAY CALCULATION

Study Day defined:

- for dates on or after date of first dose administration: (analysis date date of first dose administration) + 1.
- for dates prior to date of first dose administration: (analysis date date of first dose administration).

5.3 NUMBER OF DAYS EXPOSED TO STUDY DRUG

Based upon the pharmacokinetics of the drug (t1/2 of 18.0 to 27.0 days), each dose will count as 14 days of exposure to investigational product. Therefore, days of exposure to study drug will be calculated as:

• (last dose date – first dose date + 14).

5.4 LAST DOSE DATE

The last dose date is defined for subjects who either completed, or ET'd from, the study (i.e., have an ET visit), as the last dose administration date.

5.5 ADJUSTMENTS FOR COVARIATES

Not applicable due to the use of descriptive statistics only.

5.6 STUDY HYPOTHESES

No specific hypotheses are being tested in this pilot study. All data will be summarized using descriptive statistics only.

5.7 HANDLING OF MISSING DATA

All efforts will be made to minimize missing data.

CD patient diary data (total stools, loose/watery stools, abdominal pain, and general well-being) used in calculating the CDAI total score will handle missing data as follows: in cases where at least 4 days of data are non-missing for a given 7-day interval leading up to the visit date, the average of the non-missing values for all days in the 7-day interval will be imputed for missing diary days. If less than 4 days of data are non-missing, then the 7-day interval will be set to missing (Henao M.P., et al, 2015). To maintain consistency, the same approach of needing at least 4 days of non-missing data for imputation will also be used for UC patient diary data (stool frequency, rectal bleeding).

Missing laboratory data will not be imputed, unless otherwise stated.

All medications with partial or missing dates recorded on the concomitant medication electronic case report form (eCRF) page will be considered concomitant unless a partial stop date clearly indicates it was stopped before the first dose of study treatment. Start and stop dates will be imputed when partial dates are present as needed to determine concomitant medications.

Table 2: Table of Imputation Rules for Missing AE and Medication Date Times

Table 2. Table	of imputation Rules for i	viissing Till and ividan	cation Date Times
		Same as	
Missing Date	Prior to	Treatment Start	After Treatment Start
Portion	Treatment	Date	Date
Day	Month and Year <	Month and Year =	Month and Year >
	Month and Year of first	Month and Year of	Month and Year of first
	treatment:	first treatment:	treatment:
	Start Day = 1	Start Day = Day of	Start Day = 1
	Stop Day = last day of	first treatment	Stop Day= last day of
	the month reported	Stop Day = $last$	the month
		day of the month	
Day and Month	Year < Year of first	Year = Year of	Year > Year of first
Define Day as	treatment:	first treatment:	treatment:
above, then:			
	Start Month = January	Start Month =	Start Month = January
		Month of first	Stop Month = Dec
	Stop Month = Dec	treatment	
		Stop Month = Dec	
Day, Month, and	To be conservative, completely missing start dates will be set to the		
Year	date of first treatment, co	empletely missing end	dates will be set to the
	date of last contact.		
Time	me Missing start times will be imputed as 00:01 (or the start time		or the start time of the
	first dose administration if AE occurred on the date of first dose		
	administration)		
	Missing stop times will b	be imputed as 23:59	

After following these imputation rules, if the start date/time is imputed as a date after the end date/time, the start date/time will be set to the end date/time to provide a positive duration for the event or medication. No imputation will be done for subjects who did not receive the study drug.

Missing assessments for study medication relationship or severity for AEs starting on or after first dose administration will be analysed as related or Grade 3 respectively.

No other imputation is planned for safety data.

5.8 ASSESSMENT TIME WINDOWING

Most safety and efficacy assessment summaries will be based on the nominal protocol-specified assessment times. Thus, if the protocol specified Visit 3 (Day 7) visit occurs on study Day 8, it will still be summarized as a Visit 3 (Day 7), acknowledging that all visits after Visit 2 (Day 0) have a time window of ± 3 days.

The only exception is for daily diary data. The CD diary collects abdominal pain score, frequency of loose/watery stools, frequency of total stools, and general well-being, while the UC diary collects stool frequency and rectal bleeding. These will have 7-day interval

averages calculated, corresponding to the 7 days leading up to weekly visit dates. For screening data, the 7-day intervals will be relative to the date of first dose.

Unscheduled visits prior to first dose might be considered as the baseline value while post-baseline unscheduled visits will be listed only. Unscheduled visits are possible for biologic washout, clinical laboratory assessment, ECG, physical exam, pregnancy test, and vital signs.

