	Visit 1	Initial Phone Contact ^a	Visit for Testing Previous Biologics (if required)	Wash-out Phone Contact ^b	Visit 2 ^c		Visit 3 Day 7	Visit 4 Day 14	Visit 5 Day 21	Visit 6 Day 28	Visit 7 Day 35	Visit 8 Day 42	Visit 9 Day 49	Visit 10 / ET Visit Day 56		
					Pre-dose Day 0	Dosing and Post-dose Day 0										
Informed consent	X															
Inclusion/exclusion criteria review	X	X			X											
Testing for Previous Biologics			X ^d													
Genotyping for DcR3 genes (CD only)	X															
Demographics / medical history ^d	X															
Physical examination, incl. weight ^e	X				X			X		X		X		X		
Vital signs (BP, pulse, RR, T) ^f	X				X	X		X		X		X		X		
TB testing ^g	X															
12-lead ECG	X									X				X		
Clinical laboratory assessments ^h	X				X			X		X		X		X		

Assessment or Procedure	Screening Period				Open-Label Treatment Period										Safety Follow-up	
	Visit 1	Initial Phone Contact ^a	Visit for Testing Previous Biologics (if required)	Wash-out Phone Contact ^b	Visit 2 ^c		Visit 3 Day 7	Visit 4 Day 14	Visit 5 Day 21	Visit 6 Day 28	Visit 7 Day 35	Visit 8 Day 42	Visit 9 Day 49	Visit 10 / ET Visit Day 56		
					Pre-dose Day 0	Dosing and Post-dose Day 0										
Adverse event monitoring ^o	X	X	X	X	X	X	X	X	X	X	X	X	X	X	X	
Concomitant medications	X	X	X	X	X	X	X	X	X	X	X	X	X	X	X	
Provide/re- confirm access to subject diary	X				X		X	X	X	X	X	X	X	X		
Subject diary reviewed for completeness					X		X	X	X	X	X	X	X	X		
Assess individual subject stopping criteria						X	X	X	X	X	X	X	X	X		
MDGN-002 administration (on-site) ^p						X		X		X		X				

^a Telephone visit is conducted for confirmation of eligibility. If the subject is not currently receiving biologic treatment, they will begin completing the subject diary and have visit 2 scheduled >7 days from the diary being initiated. The diary should be completed up to the time of the visit.

^b Telephone visit is conducted for confirmation whether additional wash-out time is required following receipt and review of the laboratory results. If the concentration level is not detectable, the subject will have their visit scheduled >7 days from the time the subject started completing the diary. If the concentration level is detectable, the subject will complete the full 12 week wash-out. The diary should be completed up to the time of the visit.

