Subjects who are currently taking a biologic treatment or who have received biologic treatment within 12 weeks of the Screening Visit but who are otherwise eligible for study participation based on review of all screening evaluations and results will begin a wash-out period for these medications. Washout is the period between when the subject received their last dose of biologic and when they are eligible to proceed to Visit 2. With the exception of subjects requiring wash-out of the biologic certolizumab pegol (Cimzia), a blood test will be administered to subjects undergoing wash-out 8 weeks after their last dose of biologic treatment to ensure that serum levels of any previous biologic treatments are below the level of detection. If it is confirmed that the levels of previous biologic treatment are undetectable, then the subject will proceed to Visit 2. If the test results indicate that the previous biologic treatment is detectable, the subject will be required to complete a full 12-week wash-out period before proceeding to Visit 2. For subjects receiving the biologic certolizumab pegol (Cimzia) a 12-week wash-out is required.

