12.1.2. Eligibility Check/Wash-Out Period

Each subject will receive a telephone call to confirm continued subject eligibility. For subjects not requiring a wash-out period the subject may return for Visit 2 once the diary has been completed for a minimum of 7 days immediately prior to dosing. Visit 2 should be completed no sooner than Day 8 from the time diary completion was initiated. Any changes in concomitant medication use and any newly occurring AEs since the last evaluation will be recorded.

With the exception of subjects who most recently received the biologic certolizumab pegol (Cimzia), subjects requiring a wash-out will have a blood test administered 8 weeks after their last dose of biologic treatment to ensure that serum levels of any previous biologic treatments are below the level of detection. If it is confirmed that the levels of previous biologic treatment are undetectable and the subject has completed the diary for a minimum of 7 days immediately prior to dosing, the subject may return for Visit 2. Visit 2 should be completed no sooner than Day 8 from the time diary completion was initiated. If the test results indicate that the previous biologic treatment is detectable, the subject will be required to complete a full 12-week wash-out period. For subjects receiving the biologic certolizumab pegol (Cimzia) a 12-week wash-out is required. The diary should be completed up to the time of the visit. Any changes in concomitant medication use and any newly occurring AEs since the last evaluation will be recorded.

If the subject is not eligible, the subject should have any changes in concomitant medication use and any newly occurring AEs since the last evaluation recorded and should be removed from screening.

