12.1.5.6. Visit 10 (Day 56 [\pm 3 days])

Subjects will return to the clinic on Day 56 (\pm 3 days), at which time the following procedures will be performed:

1. Perform a complete physical examination, including measurement of weight
2. Collect vital signs, including systolic and diastolic blood pressures, pulse, respiration rate and temperature
3. Perform 12-lead ECG
4. Collect blood sample for clinical laboratory tests
5. Collect blood samples for plasma MDGN-002 concentration, PK and ADA analysis
6. Collect blood sample for exploratory analyses as defined in [Table 1](#)
7. Collect stool for fecal calprotectin analysis
8. Collect urine sample for urinalysis
9. Collect urine sample for urine β -hCG test (for females of childbearing potential only)
10. Administer the CDAI (CD only)
11. Review diary completion
12. Administer IBD-Q questionnaire
13. Conduct the endoscopy and biopsy
14. Calculate the Modified Mayo Score (excluding the PGA component) using the endoscopy score from the central reader and the diary data on stool frequency and rectal bleeding (UC only)
15. Assess and record any AEs and concomitant medications
16. Assess subject response and available results against individual stopping rules criteria defined in [Section 8.5.1](#).

In addition, ongoing AEs from the previous visit will be assessed and any change in their status will be recorded.

NOTE: Stool samples may be obtained at any time during the visit.

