12.3.3.3. Endoscopy with Biopsy and Histology

All subjects who enroll in the study will undergo an endoscopy with biopsy at screening and again at Day 56 (Visit 10) or at early termination. Screening endoscopies may be performed either as a stand-alone endoscopy for purposes of this protocol or as a clinically-required endoscopy, provided consenting procedures for this study were completed prior to endoscopy.

Endoscopy evaluation for patients with CD will use the SES-CD. The SES-CD is a simple, easy-to-use endoscopic scoring system developed specifically for CD. It assesses 4 variables: size of ulcers, percentage of ulcerated surface, percentage of affected surface and the presence of narrowing across 4 categories per variable on a scale of 0 to 3 ([Daperno et al 2004](#)).

Endoscopic evaluation for patients with UC will use the Mayo Endoscopy Score. The Mayo Endoscopy Score is a simple, easy-to-use scoring system in order to evaluate ulcerative colitis stage, based only on endoscopic exploration.

Biopsies taken at screening will be assessed for histological confirmation of disease. Each subject will have screening and Visit 10/ET biopsy samples retained for evaluation of exploratory parameters (which may include but is not limited to DcR3, LIGHT, HVEM and LT β R) which may occur after trial completion. Further information on endoscopic transmission to the central reader and assessment can be found in the endoscopy manual. Information on biopsy collection requirements for exploratory parameters are found in the study sample guidelines.

12.3.3.4. Patient-reported Assessment of Well-being, Abdominal Pain and Stool Frequency (Crohn's Disease Patients)

All CD subjects who enroll in the study will be required to report their daily assessment of well-being, abdominal pain and stool frequency including loose and/or watery stools via a diary (electronic or hard copy). Abdominal pain will be assessed on a scale of 0 to 3 with higher values indicating greater pain severity. The stool frequency including number of loose and/or watery stools per day, equivalent to a score of a 6 or 7 on the Bristol Stool Scale, will be recorded. Loose stools are described as fluffy pieces with ragged edges, a mushy stool. Watery stools are described as watery, no solid pieces ([O'Donnell et al, 1990](#)).

12.3.3.5. Patient-reported Assessment of Stool Frequency and Rectal Bleeding (Ulcerative Colitis Patients)

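### The Visit 10/ET diary window runs up to a visit with endoscopy and excludes no day; if bowel-preparation stools are entered, Visit 10 stool counts, CDAI and UC stool frequency shift towards worsening

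*SAP*

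**What the plan says.** **Diary window.** SAP 5.8 says that diary items have seven-day "averages calculated, corresponding to the 7 days leading up to weekly visit dates". SAP 4.1 sums the CDAI diary items over the seven days before the visit. SAP 4.2 takes the Modified Mayo stool frequency and rectal bleeding from the seven days before Visit 10. SAP 5.7 deals only with missing days: with at least 4 recorded days, the mean of those days fills the gaps; with fewer, the interval is missing. None of these sections leaves out a day.

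**Endoscopy.** The Visit 10 procedures (Protocol 12.1.5.6) include "Conduct the endoscopy and biopsy". Protocol 12.3.3.3 has every enrolled subject "undergo an endoscopy with biopsy at screening and again at Day 56 (Visit 10) or at early termination". No other post-dose visit includes an endoscopy.

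**Baseline.** SAP 5.8 states: "For screening data, the 7-day intervals will be relative to the date of first dose". Table 1, footnote a (Protocol 8.1), concerns the eligibility call: "If the subject is not currently receiving biologic treatment, they will begin completing the subject diary", with Visit 2 more than 7 days later. Protocol 12.1.2 allows Visit 2 once "the diary has been completed for a minimum of 7 days immediately prior to dosing". For wash-out, Protocol 8.2.1 says that subjects who are "otherwise eligible for study participation based on review of all screening evaluations and results will begin a wash-out period for these medications".

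**Use of the data.** SAP 8.1.2 lists loose/watery stools, total stools, UC stool frequency and Modified Mayo at Visit 10 as secondary endpoints. It lists CDAI only for Visits 4, 6 and 8, but SAP 4.1 derives CDAI at Visit 10 and SAP 8.2.3 summarises it by visit.

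**The concern.** A diary day spent on bowel preparation records the effect of the preparation, not of the disease. The SES-CD scores the bowel from ileum to rectum (SAP 4.3), so preparation before the CD endoscopy is very likely; for UC it is less certain. The diary counts loose and watery stools by form (Protocol 12.3.3.4) and makes no exception for preparation, so a subject who follows the written instruction would enter them.

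The baseline window would usually not carry the same effect. CD and UC eligibility need the endoscopy score (Protocol 9.1, 9.3), and subjects not on a biologic start the diary at the eligibility call, so the screening endoscopy normally comes before the seven days that precede first dose. The Modified Mayo baseline is self-report from before Visit 1 (Protocol 12.3.3.2, SAP 4.2). A screening endoscopy counts only "provided consenting procedures for this study were completed prior to endoscopy", so that period too normally precedes any preparation.

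At stake is the last on-treatment reading of the symptom endpoints in a signal-finding study with 4, 4 and 6 subjects. The shift would look like a worsening from Visit 9 to Visit 10, at the time point paired with the endoscopic endpoints.

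**Working it through.** The documents give no figure on this point, so there is none to reproduce. The sizes follow from the scoring rules and stated assumptions.

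**Inputs from the documents:** CDAI item 1 (liquid stools) is a seven-day sum with weight 2 (SAP 4.1); the 4-of-7 imputation rule (SAP 5.7); UC stool frequency is scored 0 to 3 per day (SAP 4.2); 4 CD subjects per cohort and 6 UC subjects (Protocol 8.7).

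**Assumptions:** one preparation day inside the window and recorded; *x* = 0 to 15 extra loose stools entered on it (0 = none entered); abdominal pain and well-being held constant, so only item 1 of the CDAI moves. Let *k* be the number of recorded days of 7.

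**CD, per subject.** Stools/day shift = x/k. CDAI shift = 2 × 7 × x/k.

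| x | k = 7: stools/day | k = 7: CDAI | k = 4: stools/day | k = 4: CDAI |
|---|---|---|---|---|
| 0 | 0 | 0 | 0 | 0 |
| 5 | 0.71 | 10 | 1.25 | 17.5 |
| 10 | 1.43 | 20 | 2.50 | 35 |
| 15 | 2.14 | 30 | 3.75 | 52.5 |

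The k = 4 figures are larger because the mean that includes the preparation day is also imputed to the three missing days.

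**CD, cohort mean of 4, full diary.** Shift = (m/4) × 2x for m affected subjects. With x = 10: 5, 10, 15, 20 points for m = 1 to 4. With x = 15: 7.5, 15, 22.5, 30.

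**Severity bands (SAP 4.1).** A shift of 30 points is 30/70 = 43% of the width of the mild band (150–219) and would move a true CDAI of 120–149 from remission to mild. A shift of 10 points does so for 140–149.

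**UC stool frequency.** If the preparation day scores 3 and the usual score is s, the shift is (3 − s)/k.

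| usual s | k = 7 | k = 4 |
|---|---|---|
| 0 | 0.43 | 0.75 |
| 1 | 0.29 | 0.50 |
| 2 | 0.14 | 0.25 |
| 3 | 0 | 0 |

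Each affected subject adds at most 0.43/6 = 0.07 (full diary) or 0.75/6 = 0.125 (4 recorded days) to a mean of 6. The Modified Mayo stool component shifts by the same amount if it is the unrounded seven-day mean; SAP 4.2 does not say how days are combined.

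**Illustration with assumed values.** Baseline 5 loose stools/day, true Visit 10 value 4/day, one preparation day with 10 extra. As planned: (6 × 4 + 14)/7 = 5.43, change +0.43/day, and item 1 contributes 2 × (38 − 35) = +6 to the CDAI change. With that day set to missing: mean 4.0, change −1.0/day, contribution 2 × (28 − 35) = −14. A real improvement would be tabulated as a slight worsening.

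**The case against.** The causal step lies outside the documents. They do not mention bowel preparation, its timing, or how subjects enter its stools. Protocol 12.3.3.3 refers to an endoscopy manual that is not supplied, and the diary instructions to subjects are not supplied either; either may already deal with preparation days. This stands. A reader might infer that the Visit 10 data are biased; the documents show only that the SAP window would pass such a bias through.

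The larger figures need unlikely combinations: +52.5 points needs 15 extra stools, exactly 4 recorded days, and the preparation day among them. This also stands. The shift is zero if the stools are not entered, if a UC subject usually scores 3, or if the endoscopy is so long after the recorded visit date that preparation falls outside the window (Protocol 12 lets sites adjust the order of procedures). Some early-termination subjects may have no endoscopy, since Protocol 9.6 asks for the Visit 10 evaluations only where feasible.

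Cancellation against baseline cannot be excluded for everyone. Wash-out is counted from the last biologic dose (Protocol 8.1, 8.2.1), and diary access is given at Visit 1 (Protocol 12.1.1), so no rule fixes the order of endoscopy and baseline diary for every wash-out subject.

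Finally, no hypothesis is tested, the shift runs against the drug and so cannot create a false efficacy signal in the stool endpoints, and the by-subject diary listings (SAP 8.2.3) would show a one-day spike. That limits the consequence but does not remove it: the summary tables would still contain the distorted means.

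**Conclusion.** The point holds conditionally. The SAP uses every diary day before the one post-dose visit that includes endoscopy. If preparation falls on the day before endoscopy and its stools are entered, the stool-based results at Visit 10 move in one direction, towards worsening, and usually without a matching shift at baseline.

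Under the stated assumptions a CD subject shifts by 0 to +30 CDAI points and 0 to +2.1 stools/day with a full diary, up to +52.5 points and +3.75 stools/day in the extreme case. A UC subject shifts by 0 to +0.43, up to +0.75 with 4 recorded days. The CDAI figures cover item 1 only; any effect of the preparation day on pain or well-being would come on top.

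A reader might go further and infer that the efficacy conclusions as a whole are compromised. The documents do not support that. The primary objective is safety; the primary efficacy endpoints are endoscopic scores; neither these nor Visits 3 to 9 depend on the affected days. Visit 10 CDAI is summarised but is not a listed endpoint. The change is worth making because it is cheap and the cohorts are small. Confidence is medium because the two assumptions cannot be checked here.

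**What to change.** First check the endoscopy manual and the diary instructions for any rule on preparation days. Then, in SAP 4.1, 4.2, 5.7 and 5.8, for Visit 10/ET only, set to missing any diary day in the window that is a preparation day or the endoscopy day. Take preparation dates from the concomitant medication record where present (Protocol 10.2 requires over-the-counter products to be recorded); otherwise use the day before endoscopy. Keep the seven-day window and the existing 4-of-7 rule. Leave the Visit 1 self-report period unchanged.

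The cost is SAP wording and a comparison of diary dates with the endoscopy date. Removing one day leaves 6, so 2 further missing days are tolerated; removing two leaves 5, so 1 is tolerated. A subject with 4 recorded days who loses one, or 5 who loses two, falls below the minimum and has no Visit 10 diary value. Where the default is used and no preparation took place that day, one valid day is lost.

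Moving the window back to the latest seven eligible days would avoid that loss, but it departs from the definition used at other visits and overlaps Visit 9: by 1 or 2 days at nominal Days 49 and 56. With visits on Days 52 and 53, where 6 days are already shared, a one-day exclusion makes the two windows identical. Setting the days to missing is the smaller change.
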